## 16.4 Statistical Methods

This is a standard Phase I/II study with the goal of determining the feasibility, safety and efficacy of the use of leucine in transfusion-dependent DBA subjects. A maximum of 50 subjects will be enrolled into the study. The statistical approach will be primarily descriptive in nature.

For specific aim 1, the proportion of subjects achieving a specific response at 6 and 9 months (CR, PR, NR or progression) along with their corresponding 95% confidence intervals, will be calculated using standard methods of estimating proportions.

For specific aim 2, time-to-response (separately for CR and PR) will be analyzed using survival analysis techniques. Subjects who do not achieve CR or PR by the end of the study at 9 months will be considered 'censored for CR (PR)'. Kaplan-Meier curves will be generated and the log-rank test will be used for any comparisons with respect to time-to-CR (PR), if feasible.

For specific aim 3, the approach will be primarily descriptive. However, we may carry out some analyses if feasible. First, response status at 9 months (separately for CR and PR) will be cross-tabulated with certain subject phenotypes; a chi-square test or Fisher's exact test, as appropriate, will be used to determine if there is an association between response status and the certain phenotype. Second, time-to-response will be analyzed. Kaplan-Meier curves will be generated and the log-rank test will be used to compare phenotypes with respect to time-to-CR (PR), if feasible. Subjects who do not achieve CR or PR by the end of the study at 9 months will be considered 'censored for CR (PR)'.

For specific aim 4, the proportion of adverse events will be tabulated and their corresponding 95% confidence interval will be calculated.

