## 13.2 Transfusion Therapy During Study Drug Administration

Subjects will receive 10-15 ml/kg/transfusion, with all volumes recorded on the Case Report Forms.

**13.2.1 If the hemoglobin (Hb) is less than 8 gm/dL and there is no evidence of reticulocyte response (retic count < 0.5%), the subject will be transfused as usual.**

**13.2.2 If the Hb is greater than 8 gm/dL, the reticulocyte count is greater than 0.5% (or baseline) and the subject is clinically stable (without fever, respiratory illness, etc.), the transfusion should be held.** The subject should be followed again in 1-2 weeks and reassessment will be made to see if a response is occurring.

**13.2.3 If the Hb is between 7-8 gm/dL, the reticulocyte count is greater than 0.5% (or baseline), and the subject is clinically stable, then the subject can opt out of transfusion, based upon clinical considerations, for one week, or receive 10 ml/kg packed red blood cell transfusion so as not to**

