# Master Protocol

**14.1.2 Partial Response (PR)** - Hb < 9 gm/dL with an increase in reticulocyte count to 1% and any transfusion interval increase

**14.1.3 No Response (NR)** - No change in transfusion needs, no change in Hb or reticulocyte count

**14.1.4 Progression** - An increased transfusion requirement with increased volume or increased interval

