## 16.0 BIOSTATISTICAL CONSIDERATIONS

Response to treatment (Complete, Partial, None, Progression) will be evaluated at 6 and 9 months. Time-to-achieve a complete or partial response will be examined as well.

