### 16.2 Specific Statistical Aims of the Study (for the Data Analysis)

**16.2.1** The primary objective of the study is to estimate the proportion of complete responders, partial responders or non-responders at 9 months. These proportions will also be estimated at 6 months.

**16.2.2** To determine the time-to-first occurrence of a CR or PR. Subjects who do not achieve CR or PR by the end of the study at 9 months will be considered 'censored for CR (PR)'.

**16.2.3** To catalogue the phenotypic characteristics of the responders and non-responders at 6 and 9 months.

**16.2.4** To examine the frequency and severity of adverse events (AEs) that may arise from the study and to determine if these AEs are related to the study drug.

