# Master Protocol

- a. Complete response (CR): Hb > 9 gm/dL and transfusion-independence as defined in DBA
- b. Partial response (PR): Hb < 9 gm/dL and increased reticulocyte count to greater than 1% and any increase in transfusion interval from baseline. (Baseline reticulocytes range from 0.1 to 0.5 and transfusions are usually performed every 3 weeks. An increase of reticulocyte counts to over 1 to 1.5% and any increase in transfusion interval will be considered a PR.)
- c. No response (NR): no change in transfusion requirements and no significant change in Hb or reticulocytes (or any response that does not satisfy the conditions of either a PR or CR)
- d. Progression: worsening of disease as defined by the need for more frequent transfusions

Secondary outcomes include time-to-occurrence of either a PR or CR, and safety parameters such as type, frequency, and severity of adverse events and relationship to leucine (according to the NCI CTCAE version 4.0).

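### The response categories behind the primary proportions are defined inconsistently across 14.1, 16.2.1 and 16.3, and 16.4 sets no denominator or rule for early leavers

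*Combined protocol and SAP*

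**What the plan says.** Section 16.0 states: "Response to treatment (Complete, Partial, None, Progression) will be evaluated at 6 and 9 months". Section 16.3 makes the type of response at 9 months (and 6 months) the primary outcome and introduces a list from which a subject's response is one item. Section 16.4, aim 1, reports "the proportion of subjects achieving a specific response at 6 and 9 months (CR, PR, NR or progression"), that is, four proportions: complete response (CR), partial response (PR), no response (NR) and Progression. Section 16.2.1 words the primary objective with three groups, to "estimate the proportion of complete responders, partial responders or non-responders at 9 months".

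The categories are defined twice, in 14.1 and in 16.3:

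- **Progression.** Section 14.1.4: "An increased transfusion requirement with increased volume or increased interval". Section 16.3d: "worsening of disease as defined by the need for more frequent transfusions".
- **PR.** Section 14.1.2 asks for haemoglobin below 9 gm/dL with "an increase in reticulocyte count to 1% and any transfusion interval increase". The main text of 16.3b asks for a reticulocyte count above 1%, and its parenthesis gives a range, over 1 to 1.5%. Both sections require a longer transfusion interval.
- **NR.** Section 14.1.3 describes a subject with no change. Section 16.3c adds a catch-all: "or any response that does not satisfy the conditions of either a PR or CR".

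On conduct, section 13.2 says "Subjects will receive 10-15 ml/kg/transfusion, with all volumes recorded on the Case Report Forms". Under 18.4.4, an occurrence that leads to more frequent transfusion than before the study is a serious adverse event (SAE). Under 13.5.3, a subject with a possibly related SAE is removed. Sections 15.1 to 15.4 give further routes out, and section 9.0 allows an enrolled subject who fails a laboratory recheck to go untreated. Section 16.4 refers only to subjects. It names no analysis set and does not say how to classify a subject with no 6- or 9-month assessment.

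**The concern.** The primary result of this single-treatment, open-label study is a table of proportions. Its meaning depends on three things the plan leaves open: which section's definitions apply, whether Progression is part of NR or separate from it, and who is in the denominator. If these are settled after the data are seen, the choice can move the reported rates. Section 16.5 says the results may help to estimate an effect size for a later trial, so the rates may be reused.

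The denominator matters more than usual because leaving can be linked to the outcome. A subject who needs more frequent transfusion meets an SAE definition and, if the event is judged possibly related, leaves the study. That subject may then be absent from the 6- or 9-month reading in which Progression would be counted.

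**Working it through.** **1. The plan's own figure.** Section 16.5 gives ±13.9 points for n = 50. The half-width is 1.96 × √(0.5 × 0.5 / 50) = 0.1386, so the interval is 36.1% to 63.9%. The figure reproduces. It assumes that all 50 subjects are in the denominator. It is the widest case; at a proportion of 20% the same formula gives 1.96 × √(0.2 × 0.8 / 50) = 0.111, or 11.1 points.

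**2. The definitions side by side.**

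| Subject | Under 14.1 | Under 16.3 |
|---|---|---|
| Need rises, shown by volume; interval unchanged | Progression (14.1.4) | NR (16.3c), since 16.3d looks only at frequency |
| Need rises, shown by a shorter interval; volume unchanged | Not Progression on the literal wording, unless interval is a slip for frequency or volume means total volume over time | Progression (16.3d) |
| Hb below 9 gm/dL, longer interval, reticulocytes risen to exactly 1% | PR (14.1.2) | Not PR on the main text of 16.3b; NR by the catch-all |

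The first row can arise within the protocol. The range in 13.2 is 10 to 15 ml/kg per transfusion, and 15/10 = 1.5, so volume can rise by half at an unchanged interval. The row applies only if that rise reflects increased need.

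**3. Progression nested in NR, or separate.** Assume 50 subjects: 10 CR or PR, 5 Progression, 35 others.

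- Progression nested in NR, as 16.3c reads literally and as the three groups of 16.2.1 would allow: NR = (35 + 5)/50 = 40/50 = 80.0%.
- Progression separate, as 16.0 and 16.4 list it: NR = 35/50 = 70.0%.

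The gap always equals the Progression proportion, here 5/50 = 10.0 points.

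**4. Denominator.** Assume 10 responders seen at 9 months among 50 treated. Exact (Clopper-Pearson) 95% intervals are in brackets.

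- All treated: 10/50 = 20.0% (10.0 to 33.7).
- Assessed only, 5 leavers: 10/45 = 22.2% (11.2 to 37.1).
- Assessed only, 10 leavers: 10/40 = 25.0% (12.7 to 41.2).
- Assessed only, 15 leavers: 10/35 = 28.6% (14.6 to 46.3).

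**5. Progression among those assessed.** Assume 5 of 50 worsen (10.0%) and k of them are removed before the visit. The assessed-only figure is (5 − k)/(50 − k): 4/49 = 8.2% for k = 1, 2/47 = 4.3% for k = 3, and 0/45 = 0% for k = 5.

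The documents give no dropout, response or worsening rate for this trial. All counts in steps 3 to 5 are assumptions chosen to show scale.

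**The case against.** The strongest reply is that a sensible reader can resolve most of this.

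- **Single category.** Section 16.3 introduces its list as alternatives, one per subject. A reader might infer from the catch-all that subjects are counted twice, so that the step 3 counts sum to (10 + 40 + 5)/50 = 110%. The documents do not support that, because single assignment is clearly intended. What remains open is whether Progression sits inside NR or beside it.
- **Interval wording.** Section 14.1.4 is conditioned on an increased requirement. A reader might infer that partial responders will be classed as Progression because their interval lengthens. That does not follow: a longer interval without more volume is not an increased requirement, and the word is probably a slip for frequency. The slip still needs correcting, and the difference over volume remains.
- **Denominator.** Section 16.4 mentions a maximum of 50 enrolled, and 16.5 uses n = 50, so all enrolled is the natural reading. A reader might infer that the plan will drop leavers and inflate response. It proposes no assessed-only analysis, but it does not exclude one. The 50 is an accrual cap and a precision illustration, not a stated analysis set.
- **Removal of worsening subjects.** It requires a judgement that the SAE is possibly related; otherwise 13.5.3 only pauses the drug. No frequency is given, so under-counting is possible, not established. Worsening would also still appear in the adverse event tables.
- **Time to response.** A reader might infer that aim 2 needs a competing-event analysis. Time to response is a secondary outcome, and that is a choice of method. Only the censoring time for early leavers is unstated.

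**Conclusion.** The point holds in a limited form. The definitions of Progression, PR and NR in 14.1 and 16.3 differ, and the number of categories differs between 16.2.1 and the rest of section 16. The primary proportions therefore depend on which text is followed. The missing denominator and leaver rule is a real gap, made more relevant by the link between 18.4.4 and 13.5.3.

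On the assumed counts, NR moves by 10 points and the response proportion by 2.2 to 8.6 points. Progression among those assessed could fall from 10.0% to anywhere between 8.2% and 0%, if worsening subjects are selectively removed and only assessed subjects are counted. The shifts in NR and response are modest beside the planned precision. The analysis is descriptive, with no test or decision threshold, so error rates and power are not affected. What is at stake is the meaning and comparability of the reported rates. The wording should be settled before analysis.

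**What to change.** 1. **Definitions.** Reconcile 14.1 and 16.3 so that one set applies. It should settle the direction of the interval for Progression, whether volume counts, and the reticulocyte wording for PR. The sponsor chooses the clinical content.
2. **Categories.** Add the words 'and not Progression' to the catch-all in 16.3c, and list the same four categories in 16.2.1 as in 16.0 and 16.4.
3. **Denominator, 16.4 aim 1.** Use all enrolled subjects who took at least one dose. Count a subject with no 6- or 9-month assessment as not a responder at that visit, on a separate line for those who left before it, with the reason (including increased transfusion need). The four categories and this line then sum to 100%. Give evaluable-only proportions as a sensitivity analysis.
4. **Supplementary proportion.** Tabulate Progression at any time by 9 months for all treated subjects. Retained subjects and leavers are then treated alike, and the 9-month categories still describe the state at 9 months.
5. **Aim 2.** At most, state the censoring time for early leavers. No other change is needed.

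The cost is wording in 14.1 and section 16. No new visits or data are needed, because 12.2.3 already collects transfusion dates and amounts. The downside is that the reported response rate may be lower than an evaluable-only figure: a subject in CR who leaves at month 8, for example, is not a responder at month 9. The separate line and the sensitivity analysis make that visible.

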### 13.5.3 Dose Discontinuation

In the event of any serious adverse event (SAE), the study drug will be discontinued until all symptoms resolve. If the SAE is deemed possibly related to the protocol therapy, the subject will be removed from the study and leucine will be permanently discontinued.

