## 15.0 WITHDRAWAL AND OFF STUDY CRITERIA

**15.1 Subject's choice:** A subject may withdraw from the study at any time. The risk of withdrawing will be discussed, as will alternative treatment options. Once off study, subjects will be referred back to his or her referring physician. Alternative treatment will then be discussed with the primary hematologist.

**15.2 PI Decision:** Alternative treatment options will be discussed with the subject, who will then be referred back to his or her referring physician.

**15.3 Discontinuation for Toxicity:** Subjects will be discontinued from study for any Grade III/IV toxicity related to the study drug as determined by PI.

**15.4 Discontinuation for Non-Adherence:** Subjects will be discontinued from study if non-adherent to protocol.

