# Master Protocol

provided by the Department of Defense Telemedicine and Advanced Technology Research Center (TATRC); it is not based on any formal power calculations. Results from this study may provide valuable information for quantifying the effects of leucine in this group of transfusion-dependent DBA subjects and may be useful in estimating the effect size necessary for appropriately designing future larger-scale Phase III clinical trials. However, in order to have some idea as to the precision of estimates that can be obtained from this study, when the sample size is 50, a two-sided 95% confidence interval for a single proportion using the large sample normal approximation will be no wider than  $50\% \pm 13.9\%$  i.e. the 95% confidence interval will range from at most, 36.1% to 63.9%.

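### The Kaplan-Meier curves for time to response have no rule for subjects removed before month 9; censoring them at removal would overstate the share of enrolled subjects who respond

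*Combined protocol and SAP*

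**What the plan says.** For specific aim 2, Section 16.4 states that "time-to-response (separately for CR and PR) will be analyzed using survival analysis techniques" and that "Kaplan-Meier curves will be generated and the log-rank test will be used for any comparisons with respect to time-to-CR (PR), if feasible". Aim 3 repeats the approach to compare phenotypes. The censoring rule is the same in both aims and in Section 16.2.2: "Subjects who do not achieve CR or PR by the end of the study at 9 months will be considered" censored for that response.

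Subjects can leave before month 9 by several routes. Under Section 13.5.3, if an SAE is judged possibly related, "the subject will be removed from the study and leucine will be permanently discontinued"; any other SAE only interrupts the drug until symptoms resolve. Section 15 adds the subject's own choice (15.1), the PI's decision (15.2), drug-related Grade III/IV toxicity (15.3) and non-adherence (15.4: "Subjects will be discontinued from study if non-adherent to protocol").

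No section gives a censoring time for these subjects, treats removal as a competing event, or names a cumulative incidence estimate. Section 16.3 lists time to response as a secondary outcome, and Section 16.4 calls the approach mainly descriptive.

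**The concern.** The written rule fits a subject who reaches month 9 without a response. For a subject who leaves at month 3 the analyst must choose, and the usual choice is to censor at the last observation. The documents point that way: Section 15.1 sends subjects who go off study back to their referring physician, and no later response assessment is described.

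Censoring at removal gives the removed subject, in effect, the later response rate of those who stayed. One minus Kaplan-Meier then no longer estimates the share of enrolled subjects observed to respond on leucine.

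Removal may also be related to prognosis. Section 18.4.4 makes a more frequent need for transfusion an SAE, and Section 16.3 defines progression in similar terms. If such an event is judged possibly related, a worsening subject leaves the risk set.

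The curve would then read too high, and more so with more removals. Section 16.5 says the results may help set the effect size for a later Phase III trial, so a reader could carry the higher figure forward.

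**Working it through.** **Inputs from the documents.** The trial has a single treatment and at most 50 subjects (Section 16.4). Follow-up on leucine is 9 months, and response is formally evaluated at 6 and 9 months (Section 14.1). Section 16.5 gives a precision figure.

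**Assumed inputs.** The documents give neither a response rate nor a removal rate. Let *r* be the proportion of enrolled subjects who respond by month 9 and *d* the proportion removed without response. The main case is r = 20% with d = 10%, 20% or 30%; r = 10% and 33% serve as a range.

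**Step 1: the plan's own figure.** For n = 50, the largest two-sided 95% half-width is 1.96 × √(0.25/50) = 0.1386, so 50% ± 13.9%, or 36.1% to 63.9%. This reproduces Section 16.5. The plan states no figure for the Kaplan-Meier analysis.

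**Step 2: removals and responses spread over time.** With constant cause-specific hazards and censoring at removal,

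1 − KM = 1 − (1 − r − d)^(r/(r + d)).

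- d = 10%: 1 − 0.70^(0.20/0.30) = 21.2%
- d = 20%: 1 − 0.60^(0.20/0.40) = 22.5%
- d = 30%: 1 − 0.50^(0.20/0.50) = 24.2%

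**Step 3: upper bound, with all removals before all responses.** Here 1 − KM = r/(1 − d). Take 50 subjects with 10 responders at month 6, and 5, 10 or 15 removed in months 1 to 5:

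- 10/45 = 22.2%
- 10/40 = 25.0%
- 10/35 = 28.6%

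**Step 4: removed non-responders kept at risk to month 9.** 1 − KM = 10/50 = 20.0% in every case, so the excess is zero.

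**Summary for r = 20%:**

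| Removed without response | Constant hazards | All removals first | Excess (points) |
|---|---|---|---|
| 10% | 21.2% | 22.2% | 1.2 to 2.2 |
| 20% | 22.5% | 25.0% | 2.5 to 5.0 |
| 30% | 24.2% | 28.6% | 4.2 to 8.6 |

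**Range over r = 10% to 33%.** At 10% removed, the excess runs from 0.6 points (r = 10%, constant hazards) to 3.7 points (r = 33%, all removals first). At 20% removed, it runs from 1.2 to 8.2 points.

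**Where between the two columns the trial would fall.** If response is dated only at the 6- and 9-month evaluations, most removals could precede the first event and the result moves toward the upper bound. If response is dated at the monthly visits, it moves toward the constant-hazard column. The plan does not say which dates are used.

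**The case against.** The strongest reply is that the plan nowhere says removed subjects are censored at removal. Read literally, the month 9 rule can cover every subject without a response by then, including those removed, and Step 4 shows no excess under that reading. This stands. What can be shown is a missing rule; the upward bias depends on how the gap is filled.

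Censoring at removal can also be defended. If the target were the response rate had everyone stayed on leucine, and removal were independent of response, Kaplan-Meier would be a proper estimator. The plan states no such target, and Section 18.4.4 makes independence doubtful.

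The size is modest as well. Section 6.5 describes oral leucine as having very low toxicity, so removals may be few. At 10% removal the excess is small beside 13.9 points.

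A reader might infer four stronger claims that the documents do not support:

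- *Removed subjects can no longer respond.* Section 5.1 reports remissions in up to 20% of patients. They can no longer be observed to respond on leucine, which is a narrower statement.
- *Every SAE removes a subject.* Section 13.5.3 does so only for those judged possibly related.
- *A gap between the aim 1 proportion and the curve proves bias.* Aim 1 classifies response at 6 and 9 months, while aim 2 counts first occurrence. A response can be lost, so the two may differ under any estimator.
- *Phenotypes with more removals will look more responsive, so the log-rank test is wrong.* If two phenotypes respond at the same rate while on leucine and removal is independent, the log-rank test shows no difference in expectation. Gray's test answers a different question.

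**Conclusion.** The point holds as a conditional one. Section 16.4 leaves the handling of early removals open. The usual default gives a curve that can never lie below the cumulative incidence of response, and that lies above it whenever a removal precedes a response.

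With an assumed 20% response, the month 9 reading would be about 21.2% to 24.2% for 10% to 30% removed under constant hazards, and at most 22.2% to 28.6%. The last of these needs both 30% removal and every removal before every response, so it is a bound and not an expectation. The excess is small beside the stated precision at 10% removal, deserves attention at about 20% or more, and is zero if removed subjects stay at risk to month 9. All of these sizes rest on assumed rates.

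The outcome is secondary and descriptive. The primary 6- and 9-month proportions do not use Kaplan-Meier and are untouched.

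**What to change.** In Section 16.4, for the aim 2 and aim 3 curves:

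1. State what happens to a subject who leaves leucine or the study before responding.
2. Treat that removal as a competing event and report the Aalen-Johansen cumulative incidence of first response. Keeping removed non-responders at risk to month 9 gives the same result when there is no other loss; the curve then ends at responders divided by subjects enrolled.
3. Reserve ordinary censoring for administrative loss.
4. Report the removals by date and reason.

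The log-rank test may stay, described as a comparison of response rates among those still at risk. Gray's test is optional.

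The cost is SAP wording, a slightly lower curve, and the need to record removal dates and reasons. The data items listed in Section 12 do not name these, and the case report form is not available to show whether they are already collected.
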